**Study design:**

We will conduct a pretest/posttest, randomized, placebo controlled phase 2 efficacy study on 130 subjects with vulvodynia, with high scientific rigor. In this adequately powered study, we will compare two groups (penetrating acupuncture needle [treatment] group and skin touch needle [placebo] group) in a 13-needle, 10-session acupuncture protocol delivered twice/week for 5 weeks for effects on vulvar pain (primary outcome), and dyspareunia and sexual function (secondary outcomes). Subjects will be stratified by type of vulvodynia (generalized or provoked) and randomized 1:1 either to the penetrating needle group or the skin touch placebo needle group. These double-blind needles will provide a strong

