Only four studies, including one of ours, provide some evidence of the effect of acupuncture on vulvodynia. In three, single-group acupuncture studies, women had less pain, better quality of life, improved sexual health, and improved mental health. Our randomized wait-list controlled pilot study of 36 women with vulvodynia showed great promise. We found a statistically significant and clinically meaningful reduction in vulvar pain and dyspareunia, and an increase in overall sexual function after a 5-week, 13-needle, 10 session acupuncture protocol. This newly developed, standardized acupuncture treatment protocol is the first breakthrough in the treatment of this puzzling disorder. It includes acupuncture points that relieve pain in the genitals. The results of our initial pilot study provided the first evidence from a two-group design that the acupuncture protocol could reduce pain intensity, pain during intercourse, and increase overall sexual function. Our findings, however, warrant stronger evidence to support the inference that the effect is indeed due to the acupuncture since ours or no other study included a sham control or provided follow-up data beyond immediate posttest, which means that the duration of the acupuncture effect is unknown. Our recent feasibility study paves the way to overcome this gap by use of double-blind acupuncture needles. Findings from these two studies support our proposal for the world's first double-blind randomized controlled trial (RCT) of acupuncture for vulvodynia while exploring its duration of effect.

We will conduct a phase 2 double-blind, pretest/posttest RCT to compare effects of penetrating needles or the skin touch placebo needles on vulvar pain in our 13-needle, 10-session acupuncture treatment protocol. A sample of up to 130 women, with a diagnosis of vulvodynia, either generalized or provoked vestibulodynia, will be recruited. Subjects will be stratified by type of vulvodynia, and will be randomized 1:1 either to the penetrating needle group or the skin touch placebo needle group. These double-blind needles will provide a strong sham procedure (placebo) to mask both the acupuncturist and subject to the type of needle used for the 10-treatment protocol.

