**Subject identification, recruitment and consent:**

The subjects will be women with a diagnosis of vulvodynia, who are 18 – 45 years of age. Potential participants will be recruited from clinical and community settings in Chicago, such as the UIC campus and surrounding communities, gynecologists, certified nurse-midwives, family physicians, and women's health physical therapy practices. Recruitment will also be conducted via a link on the National Vulvodynia Association (NVA) website. We will also recruit through social media like Facebook, in addition to through phone calls and emails. We plan on recruiting up to 130 women to ensure that we have full data on 80 subjects after screening and attrition. We will strive to enroll a racially and ethnically diverse sample of women.

The consent process will be completed at the UIC College of Nursing. It may also be completed at another UIC or other private location chosen by the potential subject to go over the details of the study and informed consent. All study procedures will be conducted at the UIC College of Nursing in fully equipped, clinical research exam rooms on the second floor. The screening gynecological screening exam will take place in one of the exam rooms in the CON or at [name] office in the UIC hospital.

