**Procedures:**

The research specialist (RS) will determine initial eligibility by screening potential participants during an initial telephone or in-person interview according to the inclusion and exclusion criteria. Women deemed to be eligible and interested in participating will be scheduled to go over the consent process and will then receive a gynecological screening exam by [name], a urogynecologist with expertise in changes in pelvic floor tissue related to vulvodynia, or [name], a practicing certified nurse-midwife with over 29 years of experience and a practicing acupuncturist specializing in the treatment of vulvodynia patients for 15 years. This exam will confirm the diagnosis and subtype of vulvodynia (provoked or generalized). Potential participants will also be asked to insert and remove a tampon as a standardized stimulus to provoke vulvodynia pain and women will be eligible if they report a pain level of 4 or higher. We will always use a regular size Tampax™ tampon with applicator as part of the standardized procedure. Participants determined to be ineligible after the above steps will not be able to continue study participation.

Based on the gynecological exam results, participants will be assigned to the generalized or to the provoked vulvodynia group. Eligible women will be able to start the study procedures immediately or at a future visit. Right before the first acupuncture session and once a week before an acupuncture treatment, a urine pregnancy test will be administered. If it is positive, the subject will be discontinued from the study.

Participants will be assigned at random to the experimental group, who will be treated with penetrating needles, or the control group, where the needles have a blunt tip that pinches but does not penetrate the skin. The special needles used in this study are inside an opaque insertion tube so that both the acupuncturist and participant remain blind to group assignment. The actual acupuncture needles,

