**Sample size:**

We plan to recruit 130 women to ensure that we obtain full data for 80 subjects.

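### Does calling this an adequately powered study on 130 subjects misstate the size that carries the power, when the target is 80 women with full data?

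*Combined protocol and SAP*

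**What the plan says.** The Study design section describes the trial as "We will conduct a pretest/posttest, randomized, placebo controlled phase 2 efficacy study on 130 subjects with vulvodynia" and continues "In this adequately powered study, we will compare two groups". Subjects are then stratified by vulvodynia type and "randomized 1:1 either to the penetrating needle group or the skin touch placebo needle group".

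Three other sections treat 130 as a recruitment number:

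- Background and Purpose: "A sample of up to 130 women, with a diagnosis of vulvodynia" is to be recruited.
- Subject identification, recruitment and consent: "We plan on recruiting up to 130 women to ensure that we have full data on 80 subjects after screening and attrition".
- Sample size, in its only sentence: "We plan to recruit 130 women to ensure that we obtain full data for 80 subjects".

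The Procedures section places the gynecological exam and the tampon test after the consent discussion, and adds: "Participants determined to be ineligible after the above steps will not be able to continue study participation". The Data analysis section handles missing data by intention to treat with full information maximum likelihood (FIML). Aim 1 compares the arms at posttest, controlling for baseline values.

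The documents do not give the number to be randomised, the split of losses between screening and attrition, or the alpha, power, between-group difference and SD behind the power statement.

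**The concern.** Read alone, the Study design section suggests 130 women randomised, 65 per arm, with the power claim resting on that number. The recruitment section counts 130 before screening and dropout and expects 80 with full data, which is 40 per arm if they divide evenly. Women who fail screening supply no posttest value. If any do fail, 130 cannot be the number that carries the power.

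The stake is how a null result would be read. Someone who credits the trial with 65 per arm would think it more sensitive than it is planned to be, and could take a non-significant difference as good evidence that penetrating needles do no better than the placebo needles. Background and Purpose presents this as the first double-blind randomised trial of acupuncture for the condition, so that reading would carry weight.

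**Working it through.** **The plan's own figure.** There is none to reproduce. The power claim comes without alpha, sidedness, power, effect size or SD. Only the recruitment arithmetic can be checked: 130 − 80 = 50, and 50/130 = 38.5% lost to screening and attrition combined.

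**Could the choice between 80 and 130 matter?** Assume a two-sided 5% level, 80% power, equal arms and no baseline adjustment. The detectable standardised difference is approximately

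d = (1.960 + 0.842) × √(2/n per arm)

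- 40 per arm: 2.802 × √0.0500 = 0.63
- 65 per arm: 2.802 × √0.0308 = 0.49

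The exact t-test calculation gives 0.634 and 0.495. For a true difference of 0.5 SD, t-test power is 60% with 40 per arm and 81% with 65. So the choice could decide whether the claim of adequate power is true.

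**Effect of the planned baseline adjustment.** Aim 1 controls for baseline, so the unadjusted figure understates the planned comparison. Multiplying 0.634 by √(1 − r²), for an assumed pretest–posttest correlation r, gives at 40 per arm:

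| Assumed r | √(1 − r²) | Detectable difference (SD) |
|---|---|---|
| 0.3 | 0.954 | 0.61 |
| 0.5 | 0.866 | 0.55 |
| 0.7 | 0.714 | 0.45 |

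At r = 0.7, 40 per arm with adjustment detects a smaller difference than 65 per arm without it (0.45 against 0.50 SD).

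**In points on the 0–10 scale.** The documents give no SD and no between-group target. The 1.5 points in Aim 2 is a within-woman change that selects women for follow-up, so it serves here only as an illustration. Unadjusted t-test power for a 1.5-point difference between arms:

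| Assumed SD | 40 per arm | 65 per arm |
|---|---|---|
| 2.0 | 91% | 99% |
| 2.5 | 76% | 92% |
| 3.0 | 60% | 81% |

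At 40 per arm, 80% power for 1.5 points needs an SD of at most 1.5/0.634 = 2.36 unadjusted, or 2.36/0.866 = 2.73 at r = 0.5. Whether 80 women suffice therefore depends on inputs that the documents do not contain.

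**Which size is analysed?** It need not be either 80 or 130. Under intention to treat with FIML the analysis set is the women randomised. To end with 80 complete, that is 80/(1 − attrition): 89, 100 or 115 at assumed attrition of 10%, 20% or 30%. Women with only a baseline value add little to the posttest contrast, so 80 remains a reasonable guide to precision, but it is not the planned analysis set.

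**The passages side by side.** Three sections use 130 as the number recruited. Two of them give 80 as the number with full data, and one explains the gap by screening and attrition. Only the Study design section speaks of a study on 130 subjects, and it does not say that 130 are randomised, that 130 are analysed, or that the power rests on 130.

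**The case for a change.** The strongest case for a change is that the power claim directly follows the figure of 130, with 1:1 randomisation after it, so a reader of that section alone has no other number to attach it to. The Sample size section offers no calculation to correct that impression. A 38.5% planned loss is not small, and the remedy would be wording only: state the numbers recruited, randomised and expected with full data, and replace the claim of adequate power with the detectable difference.

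Part of this stands. The phrase is loose, and a power justification would help readers. The rest does not carry. A reader who turns to the section headed Sample size meets 80 at once. Recruiting 130 so as to secure 80 complete cases reads naturally as a trial sized on 80, with 130 as the allowance for losses.

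The replacement wording would also introduce errors. Calling 80 the planned analysed size would conflict with the intention-to-treat analysis. Writing in 0.63 SD would give the trial an unadjusted figure, at an alpha and power that it never states, for a comparison that it plans to adjust for baseline.

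**Conclusion.** No change follows. The Study design section uses the recruitment ceiling as shorthand for the size of the study, and two other sections give the target of 80 women with full data. The discrepancy of 50 women (38.5%) is real as wording, and it would matter if the power claim were shown to rest on 130. The documents do not show that, nor that 80 is too few. At an assumed two-sided 5% level and 80% power, 40 per arm detects about 0.63 SD unadjusted, or 0.61 to 0.45 SD with baseline adjustment at assumed correlations of 0.3 to 0.7. Those figures rest on assumed inputs and cannot contradict a calculation that is not reported.

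What is left is missing detail: the number to be randomised and the inputs to the power statement. Supplying it would leave the same women recruited, the same randomisation, the same baseline-adjusted intention-to-treat analysis and the same conclusion. Anyone interpreting a null result would work from the confidence interval and the numbers actually randomised and completed, which answer the sensitivity question better than either planning figure.

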**Title: DOUBLE-BLIND PHASE 2 RCT: EFFECT OF ACUPUNCTURE ON PATIENT VULVODYNIA OUTCOMES**

**RESEARCH PROTOCOL**

Dated 8/15/2017

sham procedure to mask both the acupuncturist and subject to the type of needle used. The acupuncturist will be well-trained in the study protocol and will be observed for fidelity. We will obtain measures at 2 time points (baseline and immediately post 10th acupuncture treatment [5 weeks]). Duration of effects will be measured weekly beginning one week after posttest for up to 12 weeks.

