**Title: DOUBLE-BLIND PHASE 2 RCT: EFFECT OF ACUPUNCTURE ON PATIENT VULVODYNIA OUTCOMES**

**RESEARCH PROTOCOL**

Dated 8/15/2017

Specific aims are to:

Aim 1. Compare the penetrating needle group and the skin touch placebo needle group for effects on the: (a) primary outcome: vulvar pain (PAINReportIt® average pain intensity, 0-10), and (b) secondary outcomes: dyspareunia (FSFI dyspareunia) and sexual function (FSFI total). We hypothesize that controlling for baseline values, at posttest there will be statistically significant less vulvar pain (primary) and dyspareunia and better sexual function in the penetrating needle group compared to the skin touch placebo group.

Aim 2. In subjects with a clinically meaningful reduction in pain intensity (at least 1.5 points) at posttest compared to pretest, describe the duration of the acupuncture treatment and placebo effects weekly until pain returns to pretest or up to 12 weeks after posttest. We will describe the variability over time in vulvar pain intensity (0-10) after a tampon insertion-removal stimulus and thereby explore the duration of the effect by intervention group, vulvodynia subgroups, and demographic subgroups (e.g., age, race, occupation). These findings will provide insights to guide future research on initial and maintenance acupuncture for vulvodynia.

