**Title: DOUBLE-BLIND PHASE 2 RCT: EFFECT OF ACUPUNCTURE ON PATIENT VULVODYNIA OUTCOMES**

**RESEARCH PROTOCOL**

Dated 8/15/2017

however, are regular needles used in routine acupuncture. All participants will be informed that they will receive either real or fake acupuncture and they will not be told what kind of needles they are receiving until they complete the duration of effect portion of the study. Participants in the control group will be offered 10 free real acupuncture sessions with regular (not double-blind) acupuncture needles administered by a second acupuncturist after the end of the 17 weeks. The double blind needles are manufactured by [name], the inventor of the double blind acupuncture needle, and will be sent to us sterilized and packaged to maintain sterility.

All participants will receive 10 acupuncture session, two sessions per week over an approximately 5 week period. Each session will last about one hour. The first and last sessions only, where participants will complete the study questionnaires, are expected to last an additional 30 - 60 minutes. Each acupuncture treatment will consist of 13 acupuncture points, of which 12 points specifically treat problems with the genitals. Once the 13 needles are inserted or placed on the skin in the 13 points, they will remain in place for 45 minutes. The RS will remain with the subjects during the treatment session.

At pre-test, before the first acupuncture session, and at post-test, after the 10th acupuncture treatment, participants will be asked to insert and remove a regular Tampax™ tampon with applicator as a standardized pain stimulus, and will complete the three study measures of vulvar pain and sexual function on a computer or tablet:

- 1) PAINReportIt® computerized program to assess pain intensity as well as collect demographics and medications information
- 2) Female Sexual Function Index (FSFI) to assess dyspareunia and sexual function
- 3) Vulvar Pain Functional Questionnaire to describe the physical dimension of impairment in women with vulvodynia
- 4) At post-test, participants will also complete the Double-Blind Needle Questionnaire for the participants to report whether or not they remained blinded to the type of needle used (penetrating or skin touch placebo).

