Weekly for up to 12 weeks after the 10th treatment session, the subjects will be asked to insert and remove a regular Tampax™ tampon with applicator from their vagina and complete the weekly vulvar pain diary to record their vulvar pain, so that we can determine the duration of the treatment effects.

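### The primary comparison is made in the same visit as the 10th needling, and no planned comparison of all randomised women looks at pain after that visit

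*Combined protocol and SAP*

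**What the plan says.** **When the main measures are taken.** Study design: "We will obtain measures at 2 time points (baseline and immediately post" the 10th treatment, at 5 weeks. Procedures place the questionnaires inside the treatment visits: "The first and last sessions only, where participants will complete the study questionnaires, are expected to last an additional 30 - 60 minutes". The order differs between the two occasions: "At pre-test, before the first acupuncture session, and at post-test, after the 10"th treatment. So pretest comes before any needling, while posttest, with its tampon stimulus, follows a session in which the needles stay in for 45 minutes.

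**What is tested.** Aim 1 names the "primary outcome: vulvar pain (PAINReportIt® average pain intensity, 0-10"), with FSFI dyspareunia and FSFI total as secondary outcomes. The hypothesis is tied to one time: "We hypothesize that controlling for baseline values, at posttest there will be statistically significant less vulvar pain (primary"), and likewise for the two FSFI outcomes. The Data analysis section adds no later between-arm comparison.

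**What happens afterwards.** Weekly measurement starts one week after posttest and runs for up to 12 weeks. Aim 2 restricts it: "In subjects with a clinically meaningful reduction in pain intensity (at least 1.5 points) at posttest compared to pretest, describe the duration" of the effects, weekly until pain is back at its pretest level or 12 weeks have passed. Its language is descriptive and exploratory. The diary paragraph in Procedures has no such restriction: each week "the subjects will be asked to insert and remove a regular Tampax™ tampon" and complete the diary.

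**The gap the trial names.** Background and Purpose says that no earlier study included a sham control or "provided follow-up data beyond immediate posttest, which means that the duration of the acupuncture effect is unknown".

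**The concern.** The arms are measured at the same moment, so the posttest contrast is a valid randomised comparison. The question is what it estimates. The placebo needle does not penetrate, so any short-lived relief specific to penetration occurs in one arm only and stays in the difference. It is then added to whatever has built up over ten sessions, and one post-session measurement cannot separate the two.

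This matters for the claim drawn from a positive result. A reader will take it as evidence about treating a chronic pain condition, and Aim 2 hopes to inform initial and maintenance acupuncture. Both depend on the benefit outlasting the visit. The only planned look beyond the visit is in a subset chosen by its outcome at the visit, so it no longer has the protection of randomisation.

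**Working it through.** **Inputs from the document.** 80 women with full data (Sample size) and 1:1 allocation (Study design) give 40 per arm. The 1.5-point responder threshold comes from Aim 2.

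**Inputs assumed.** SD of pain 2 to 2.5; correlation 0.5 between any two occasions; two-sided 5% test; a same-session effect of 1.5 points, borrowed from the responder threshold; a 1-point improvement in both arms (step 3 only). The document gives no alpha, power, SD or between-arm difference, so its sample size of 80 cannot be reproduced.

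**Step 1. Chance of a positive primary result when the lasting effect is zero.**

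SE = SD × √(1 − 0.5²) × √(2/40)

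- SD 2: 2 × 0.866 × 0.2236 = 0.387
- SD 2.5: 2.5 × 0.866 × 0.2236 = 0.484

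P(significant) = Φ(d/SE − 1.96) + Φ(−d/SE − 1.96), where d is the part of the 1.5-point transient effect that reaches the primary score.

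| Share entering the score | d | SD 2 | SD 2.5 |
|---|---|---|---|
| All | 1.5 | 97% | 87% |
| Half | 0.75 | 49% | 34% |
| One third | 0.5 | 25% | 18% |
| One tenth | 0.15 | 7% | 6% |

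The unstated look-back window decides the row. If the score mainly reflects pain around the tampon test, the top row is close. If it averages over many earlier days, the bottom row is, and that is near the 5% error rate.

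**Step 2. The same comparison one week later.** In a simulation of 4,000 trials under these assumptions, with the 1.5-point effect present at posttest and gone by week 1, the baseline-adjusted comparison was significant at posttest in about 97% (SD 2) and 87% (SD 2.5). At week 1 in all randomised women it was significant in about 5%. A week-1 comparison with randomisation intact therefore distinguishes the two situations.

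**Step 3. What Aim 2 would show instead.** Let C be pretest minus posttest. With all correlations 0.5, C has standard deviation SD. Its mean is 1 in the placebo arm and 1 + 1.5 = 2.5 in the penetrating arm. The regression of week-1 improvement on C has slope 0.5, and true mean week-1 improvement is 1 in both arms. Among women with C ≥ 1.5:

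mean week-1 improvement = 1 + 0.5 × SD × φ(a)/(1 − Φ(a)), with a = (1.5 − mean of C)/SD

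| SD | Arm | a | Responders | φ(a)/(1 − Φ(a)) | Mean week-1 improvement |
|---|---|---|---|---|---|
| 2 | Placebo | 0.25 | 40% | 0.964 | 1.96 |
| 2 | Penetrating | −0.50 | 69% | 0.509 | 1.51 |
| 2.5 | Placebo | 0.20 | 42% | 0.929 | 2.16 |
| 2.5 | Penetrating | −0.40 | 66% | 0.562 | 1.70 |

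The differences are 1.51 − 1.96 = −0.45 and 1.70 − 2.16 = −0.46; the simulation gave −0.44 to −0.47. The arms truly do not differ at week 1, yet the responder-only contrast makes the penetrating arm look about 0.45 points worse. Selection alone produces this.

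**The case against.** **The primary outcome may be largely protected.** It is an average pain score, and the Inclusion criteria use a different term, pain now, for the tampon-evoked rating. A reader might infer from the top row of the first table that a same-session effect would by itself make the trial positive. The document does not support that: without the look-back window, the chance runs from near the type I error rate to almost certain. The point that stands is that the plan does not rule the problem out.

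**Other randomised comparisons exist.** FSFI dyspareunia and FSFI total are compared between arms. Pain during intercourse and sexual function can hardly change between needle removal and a questionnaire in the same visit, so a pain difference with flat FSFI results would be a warning. It would therefore be wrong to say that no randomised analysis could hint at transience. But these outcomes are secondary, come from the same visit, and give only indirect evidence on duration.

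**The plan does what it says.** Demonstrating the effects of acupuncture is called a long-term goal; this is a phase 2 trial with a hypothesis at posttest and duration left to exploration. That is fair, and it is why the primary time point need not move. It does not rescue the responder-only contrast, which misleads even as exploration.

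**A week-1 test could mislabel a real effect.** A tempting rule would call the primary result immediate-only whenever week 1 is not significant. Under the same assumptions, a fully lasting 1-point effect is significant on each occasion with probability 73% (SD 2) or 54% (SD 2.5), and the two adjusted estimates correlate (0.5 − 0.25)/0.75 = 1/3. Among primary-positive trials, week 1 would then be non-significant in about 21% (SD 2) to 36% (SD 2.5). Week 1 also changes the instrument, from PAINReportIt to a diary. This objection stands in full against such a rule.

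**Conclusion.** The concern holds in a limited form. The primary contrast is valid, but it estimates same-session and accumulated effects together. Neither the FSFI outcomes nor Aim 2 as written can settle whether a difference in pain persists. The size is uncertain: for a purely transient 1.5-point effect, a positive primary result has probability 87% to 97%, 34% to 49%, or 6% to 7% as the share entering the score falls from all to half to a tenth. The Aim 2 distortion of about 0.45 points does not depend on the arms differing at week 1. All these figures rest on the assumed SD, correlation, alpha and effect sizes; the distortion also assumes that the transient effect fully enters the score that defines response. The design does not show that any effect would be transient, and it does not exclude a lasting one.

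**What to change.** 1. Keep the primary outcome and time point.
2. State the look-back window of the PAINReportIt average pain score.
3. Reconcile Aim 2 with the diary paragraph in Procedures, so that at least the week-1 tampon test and diary are collected from all randomised women whatever their posttest response.
4. Prespecify, as a secondary analysis, the between-arm difference in tampon-evoked pain (0-10) at week 1 in all randomised women, adjusted for pretest tampon-evoked pain and vulvodynia type, reported with its 95% confidence interval. Name the pretest item that serves as the covariate.
5. Interpret persistence from that estimate and interval. Do not adopt a rule that relabels the primary result as immediate-only when week 1 is not significant.

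The cost is mainly wording. Procedures already ask the subjects for the diary without restriction, so the burden is at most one more home tampon test and entry for women who did not respond. Participants are told their needle type only after the duration phase, so week 1 remains a blinded comparison for them. The price to the sponsor is that a positive primary result may support a more limited claim.
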